### **Quality control**

The researcher will guarantee the accuracy and integrity of the data, as well as all required reports. Data included in the Data Collection Booklet (DCB) that are derived from source documents will be consistent with those documents; otherwise, any discrepancies will be justified.

The investigator will retain the study documents for at least five years after the study's completion.

Upon request from the monitor, auditor, Ethics Committee, or health authority, the investigator will make all study-related files available, allowing direct access to the source data or documents for monitoring, auditing, Ethics Committee review, and trial inspection by the competent authorities.

### **Limitations of the design, the information source, and the analysis methods**

The main limitation of machine learning lies in the quantity and quality of the images collected. Variability in lighting, color, shape, size, and focus are crucial, as is the number of images per patient. This means that high variability within the same patient and an insufficient number of images to reflect that variability can result in lower-than-expected accuracy.

## **5. Work plan (tasks, milestones and study timeline)**

### **Recruitment of practitioners**

The Principal Investigator and/or the collaborating researchers assigned to this task will explain to the primary care physicians what their participation in the study will entail. The physicians will then be able to ask any questions they deem necessary to clarify any doubts they may have regarding the study. Likewise, all physicians participating in the study will receive specific information on the use of the artificial intelligence tool, provided by an expert in the field.

If the physician wishes to participate in the study, they will sign the Informed Consent form and will be assigned a study code. After signing the informed consent form, the data collection process begins.

The Principal Investigator and/or the collaborating researchers assigned to this task will collect demographic data (age, center, years in practice) and explain to the physician the steps they must follow as part of the study.

### **Patient identification.**

The primary objective of this study is to evaluate the clinical utility perceived by physicians; therefore, patients' clinical variables are not the focus of the study. Patients will be identified in the tool solely for the purpose of enabling its use, and their data will not be analyzed or processed in any way.

The primary care physician will explain the study to the patient using the Patient Information Sheet. The patient will then be able to ask any questions they may have to clarify any doubts regarding the study.

If the patient wishes to participate, they will sign the Informed Consent form and will be assigned a study code. Data collection begins after the informed consent form is signed.

The Principal Investigator and/or the collaborating researchers assigned to this task will enter demographic data (age, sex) and data related to the diagnosis, characteristics, and treatment of the pathology into Legit.Health platform.

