For several years, and as part of the objectives of utilizing new information and communication technologies (ICTs), healthcare information systems have been adapted to record certain Primary Care (PC) activities. Since June 2020, an asynchronous e-consultation for Dermatology has been available, allowing the transmission of clinical information and images generated in Health Centers to the Dermatology Department of Puerta de Hierro Majadahonda Hospital, integrated within the hospital's own information system (Selene).

The gradual implementation of teledermatology within the strategic plan of the Community of Madrid has culminated in the development of the teleDERMADRID project. Led by [name] and [name] (GAOAIO), in coordination with DGASA, this project enables a new, non-face-to-face consultation modality adapted to the current social and technological reality. This new modality includes an image acquisition management (IAM) tool, accessible via a QR code on the mobile device, which improves and streamlines the e-consultation. This tool is directly linked to the integrated request system (SIPE), ensuring rapid and generally satisfactory access to and response to the health problems of the target population, thus avoiding diagnostic delays, unnecessary travel, and expediting the therapeutic requirements available in our service portfolio.

The reduction of pressure on in-person hospital consultations directly contributes to lower costs for conventional care. All of this is achieved without compromising the humanization of patient care, another key objective for improving health-related quality of life. In addition to the image management tool, a clinical form is associated with the necessary items to complement the image.

Advancing the development of ICTs, the emergence of Artificial Intelligence in medicine has enabled the automation of a wide variety of processes, such as patient triage, allowing for faster care for those suffering from more serious conditions. The use of these types of systems by primary care physicians can increase their diagnostic capacity by up to 12%, proving highly useful in appropriate referrals for patients with skin conditions.

Therefore, this study aims to clinically validate a novel artificial intelligence tool to increase the appropriateness of referrals from primary care to dermatology.

---

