## Hypothesis

The hypothesis guiding this study is that the Legit.Health platform, developed by AI LABS GROUP SL, significantly increases the appropriateness of referrals to dermatology.

This hypothesis is based on the notion that artificial intelligence introduces several significant changes to the diagnostic process:

- Greater sensitivity and specificity than a primary care physician in diagnosing skin conditions, especially in differentiating between malignant and benign lesions.
- It provides the security of a clinically validated second medical opinion.

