## 3. Primary and secondary objectives

The main objective of this study is to validate the clinical utility of the Legit.Health platform, developed by AI LABS GROUP SL, in the management of patients with skin conditions by primary care physicians and dermatologists at the Puerta de Hierro Majadahonda University Hospital involved in the project.

Secondary objectives include:

- Reduce and correct the referral of patients with skin conditions from primary care to dermatology.
- Personalize and improve continuing education for primary care physicians in the field of dermatology.
- Offer healthcare adapted to technological innovations.
- Measure the satisfaction of primary care physicians with the Legit.Health platform.
- Measure the satisfaction of dermatologists with the Legit.Health platform.

---

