**Variables**

The main variable aims to determine the clinical utility of the platform developed by AI LABS GROUP SL in the management of patients with skin pathology by primary care physicians and dermatologists of the Puerta de Hierro Majadahonda University Hospital involved in the project.

For this purpose, clinicians will complete the **Clinical Utility and Satisfaction Questionnaire (Annex I)**.

In addition, the following secondary variables will be collected::

- Patient demographics:
  - Sex
  - Age
- Teleconsultation data:
  - Response time
  - Response label (follow-up in primary care, shared follow-up, dermatology follow-up, insufficient or inadequate information)
- Data from the in-person consultation:

- Duration of an in-person dermatology appointment to respond to an online primary care consultation.
- Waiting time until being seen in a specialized dermatology clinic.
- Diagnosis
  - Diagnostic correlation between primary care and dermatology.
  - Number of patients referred by pathology.
  - Diagnostic correlation between primary care, dermatology, and dermatopathology (if applicable).
  - Time elapsed between the day of the primary care visit and the day of the histopathological diagnosis (if applicable).
- Primary care physician satisfaction using the Clinical Utility and Satisfaction Questionnaire (Appendix I).
- Dermatologists satisfaction using the Clinical Utility and Satisfaction Questionnaire (Appendix I).

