### **Expected sample size**

This study will recruit 100 patients. This study is designed as a proof-of-concept pilot study in which the sample size has been estimated based on the number of primary care physicians who treat patients diagnosed with skin diseases who can be seen in the primary care services of the following centers:

1. Majadahonda Health Center
2. Pozuelo Health Center

During the study recruitment period, all patients diagnosed with skin diseases who meet the selection criteria will be included.

To ensure that all primary care physicians participating in the study have sufficiently interacted with the tool, a minimum of 50 patients per primary care center is required.

The data collected from these patients during the study period will be analyzed, and based on the results, an assessment will be made as to whether it is necessary to expand the sample size to include more patients.

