## **Procedures to be performed by the specialist physician**

### **1. Consultation**

The Principal Investigator will see patients while maintaining their standard clinical routine. In the Data Collection Document (DCD), they will note the appropriateness of the patient referral. If they deem the referral to dermatology inappropriate, this will also be recorded. The initial diagnosis provided by the primary care physician, as well as their own diagnosis, will be documented. If relevant, the pathology diagnosis will also be included.

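### The protocol both forbids and plans the analysis of patient data, and its hypothesis of increased referral appropriateness does not match its primary variable and cannot be tested as designed

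*Combined protocol and SAP*

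**What the plan says.** **On patient data.** Section 5, Patient identification, explains that the study is about utility as physicians see it, that patients are entered in the tool only so that it can be used, and that "their data will not be analyzed or processed in any way". Section 4, Expected sample size, says the reverse: "The data collected from these patients during the study period will be analyzed", with the results deciding whether more patients are needed. Section 4, Variables, lists patient-level secondary variables, among them "Diagnostic correlation between primary care and dermatology". In section 5, under the specialist physician's Consultation, the Principal Investigator uses the Data Collection Document, where "they will note the appropriateness of the patient referral", together with the primary care diagnosis and their own.

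**On the question being asked.** Background and rationale states that "this study aims to clinically validate a novel artificial intelligence tool to increase the appropriateness of referrals from primary care to dermatology". The Hypothesis is that the platform "significantly increases the appropriateness of referrals to dermatology". Section 3 sets a different primary target: "The main objective of this study is to validate the clinical utility of the Legit.Health platform". Referral appears there only as a secondary objective: "Reduce and correct the referral of patients with skin conditions from primary care to dermatology". The main variable in section 4 is clinical utility, measured by the Annex I questionnaire, which clinicians complete at 2 and 4 months.

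**The concern.** There are two separate defects.

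The first is a contradiction about what may be done with the data. If the Patient identification clause is obeyed, the patient-level secondary variables cannot be reported, the referral objective loses its data, and the decision on expanding the sample has no patient results to rest on. If the Variables and sample size sections are obeyed, the study does what its own protocol says it will not do. Patients sign consent in this study, so the text has to be settled.

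The second is a mismatch between hypothesis and measurement. The hypothesis claims a significant increase in referral appropriateness. The primary variable is clinicians' opinion of utility, and appropriateness is absent from the list of variables although it is recorded. A favourable questionnaire score would say nothing direct about the hypothesis, and no other listed variable fills the gap.

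**Working it through.** The point rests on text, so the statements are set side by side first. The arithmetic afterwards shows what a descriptive estimate could deliver.

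**1. Patient-level variables affected by the clause.** From section 4, Variables:

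| Group | Variables | Count |
|---|---|---|
| Demographics | sex; age | 2 |
| Teleconsultation | response time; response label | 2 |
| In-person consultation | appointment duration; waiting time | 2 |
| Diagnosis | primary care–dermatology correlation; referrals by pathology; correlation including dermatopathology; time to histopathological diagnosis | 4 |

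2 + 2 + 2 + 4 = 10. The two remaining secondary variables are clinician satisfaction, which does not use patient data. On its plain reading the clause bars all ten.

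**2. Whether a narrow reading removes the conflict.** Suppose the clause covers only data held in the Legit.Health platform. Section 5 has the primary care physician enter the diagnosis there, and Patient identification has age, sex and data on diagnosis, characteristics and treatment entered there too. The diagnostic correlations would then still draw on data first entered in the tool. The conflict becomes smaller but does not disappear.

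**3. Whether any listed variable measures the hypothesis.**
- Annex I asks for answers from experience, without consulting records. Item 7 is the nearest to referral: a 0–10 opinion on the efficiency of referrals, by disease. It does not measure appropriateness.
- Response label is a triage outcome and is not defined as appropriateness.
- Referrals by pathology is a count.
- Appropriateness itself is noted in the Data Collection Document, but with no criteria, no entry in section 4 and no analysis.

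**4. Whether an increase could be tested.** An increase needs a reference. The design is a single series in which the tool is used for the included patients, and no comparator, earlier period or baseline appropriateness rate is described.

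**5. The plan's own sample size.** Two centres × a minimum of 50 patients each = 100, which reproduces the stated total. It is a feasibility figure; no alpha, power, effect size or reference rate is given.

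**6. Precision of a descriptive proportion (illustration).** Half-width of the 95% interval = 1.96 × √(p(1 − p)/n). Neither the appropriateness rate p nor the number of referrals n is in the protocol. The values below are assumptions.

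| Referrals assessed | p = 0.5 | p = 0.8 |
|---|---|---|
| 100 | 9.8 points | 7.8 points |
| 50 | 13.9 points | 11.1 points |
| 30 | 17.9 points | 14.3 points |

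Example: 1.96 × √(0.5 × 0.5/50) = 0.139.

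**7. If a comparator were added instead (illustration).** Two equal groups, two-sided alpha 0.05, assumed baseline p₁ of 0.5 to 0.7, p₂ = p₁ + 0.10, and p̄ their mean. For 80% power, n per group = [1.96√(2p̄(1 − p̄)) + 0.842√(p₁(1 − p₁) + p₂(1 − p₂))]² / 0.10².
- p₁ = 0.5: [1.96√0.495 + 0.842√0.49]² / 0.01, giving 388.
- p₁ = 0.7: [1.96√0.375 + 0.842√0.37]² / 0.01, giving 294.

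With 100 per group the power would be 0.29 and 0.37 respectively. A study of this size could not be expected to show a 10-point rise even with a control group of equal size.

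**The case against.** The strongest reply is that the core of the design is coherent. Primary objective, main variable and instrument all concern clinical utility, which Patient identification describes as utility perceived by physicians, and section 4 calls the study a proof-of-concept pilot. Perceived utility as the primary outcome, with referral outcomes secondary, is a legitimate choice. That stands, and the point here does not dispute it. It also follows that the remark that patients' clinical variables are not the study's focus can remain, because it is compatible with secondary patient-level variables.

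A reader might infer that the plan as a whole rules out any analysis of patient data. The documents do not support that: one clause says so, while the sample size and Variables sections say the opposite. The defect is an inconsistency between two positions.

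A reader might also infer that nothing relevant to the hypothesis is captured. That too goes beyond the text. Appropriateness, including inappropriate referral, is recorded by the Principal Investigator, and a secondary objective addresses referral. The gap is narrower: the item has no definition, no listing and no analysis.

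The clause may have been meant only for data held in the tool. This softens the count of ten, since referrals are made in Selene and response and waiting times may come from there. It does not remove the conflict, as shown above.

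Finally, no passage says that a questionnaire score will be presented as confirming the referral hypothesis. The dissemination plan speaks of the survey results only. That misuse is a risk to guard against in the wording, and it should not be read as the sponsor's stated intention.

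**Conclusion.** The point holds in two parts.

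First, the protocol contradicts itself on whether patient data are analysed. On the plain reading, ten secondary variables and the expansion decision are affected; on the reading limited to the tool, at least the diagnostic correlations still are. This must be reconciled.

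Second, the hypothesis does not correspond to the primary variable, and an increase in appropriateness cannot be tested with the design described. It is tempting to conclude that listing appropriateness as a variable would make the hypothesis testable. It would not: a single proportion without a reference gives a level and cannot show a change.

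These conclusions rest on the text. Only the precision and power figures rest on assumed rates and referral numbers, and neither part depends on them. The patient information sheet was not available, so whether it agrees with either position is unknown.

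**What to change.** 1. In Patient identification, delete only the clause "their data will not be analyzed or processed in any way". State in its place that the coded patient data listed in section 4 will be analysed for the secondary objectives. The remark about the study's focus may stay. Check that the patient information sheet says the same.
2. Add to section 4, as a descriptive secondary variable: referral appropriateness (dermatologist's judgement, appropriate/inappropriate, per referral). Report it as a proportion of assessed referrals with a 95% confidence interval.
3. Reword the hypothesis to perceived clinical utility as primary, with a descriptive estimate of referral appropriateness, and make no claim of an increase. Bring the aim in Background and rationale into line.
4. State that Annex I supports conclusions about perceived utility only.

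The patient-level variables need not be dropped, and no new data collection is needed, because the Principal Investigator already records appropriateness. The cost is an ethics-committee amendment and a narrower claim. To keep a claim of increase, the sponsor would have to add a comparator or baseline and, under the assumptions above, far more than 100 patients to detect a 10-point rise.

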## **Procedures to be performed by the primary care physician**

### **1. Consultation**

Primary care physicians will need to take photographs showing the areas affected by the condition. These photographs will be taken with their own smartphone or using a mobile dermatoscope if its use is clinically relevant. Primary care physicians will upload the photographs to the Legit.Health platform.

Primary care physicians will assess the patient's condition through direct observation and guided by the results from the platform. They will enter the diagnosis into the Legit.Health platform by selecting the condition if it is among the first 5 or by using a drop-down menu that displays a wide range of conditions.

In addition to the most likely diagnoses, physicians will have access to referral criteria, the clinical referral questionnaire, and basic treatment advice. When they deem it necessary, they will refer the patient in their Selene system, as they normally would; not through Legit.Health.

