## 2. Theoretical framework. Problem statement.

### Background and rationale

Skin-related diseases are a frequent reason for consultation in primary care (PC); some studies estimate this at approximately 5% of all consultations, mainly among the working population.

This represents a considerable consumption of resources and makes an efficient approach to these conditions a key step in optimizing the functioning of primary care.

Numerous studies show discrepancies in opinion between primary care physicians and dermatologists, with agreement rates in their diagnoses ranging from 57% to 65.52% depending on the study. In general, primary care physicians do not demonstrate adequate knowledge about skin diseases, their diagnosis, and their treatments.

This human limitation when evaluating skin diseases is also reflected in the effort and time required to estimate the degree of involvement in a patient or the stage of the pathology. So much so, that it ends up being a very unrewarding task and can lead to poor adherence to the protocol and inappropriate referrals. Time consumption is especially concerning given that the number of medical professionals, particularly in dermatology, is insufficient to meet the existing demand. Access to a dermatology specialist for the general population is complicated due to the low number (3 dermatologists per 100,000 inhabitants), a situation that is even more difficult in small population centers. Because of this, screening for dermatological lesions must be carried out by primary care physicians, whose diagnostic capacity is even lower and which may increase the risk of misdiagnosis.

In this regard, the literature shows a discrepancy of between 55% and 65% between primary care physicians and specialists, and studies confirm several expected characteristics: common dermatological diseases are often not recognized or are misdiagnosed by non-dermatologists due to the particular profiles of common diagnoses in this field (drug-induced rashes, fungal infections).

In addition to these inherent limitations, when the preliminary examination is performed by the patient, the possibility of bias arises. This is especially true

when the patient knows that the treatment they receive will be determined by the information they provide. Furthermore, the medical team lacks the means to verify the accuracy of the values reported by the patient, preventing external verification.

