## 4. Methods

### Study design

This is a prospective, observational, analytical study of a series of clinical cases.

It is a longitudinal study.

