#### Inclusion criteria:

- Patients with suspected of having the following pathologies in Primary Care:
  - Tumor pathology
    - Benign
      - Histiocytoma
      - Seborrheic keratosis
      - Angiomas
    - Precancerous
      - Actinic Keratosis
    - Suspected malignancy:
      - Basal cell carcinoma
      - Squamous cell carcinoma
    - Pigmented lesions
      - Melanocytic nevus
      - Malignant melanoma
  - Inflammatory pathology
    - Psoriasis
    - Atopic dermatitis
    - Urticaria

- Hidradenitis suppurativa
- Lichen planus
- Infectious pathology
  - Viral warts
  - Molluscs
  - Herpes simplex
- Patients aged 18 years or older.
- Patients who have signed the informed consent for the study.

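### The only primary care diagnosis with a defined capture step is entered after the platform's output is shown, and no comparator is planned, so no objective gain in diagnosis or referral can be attributed to the tool

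*Combined protocol and SAP*

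**What the plan says.** - **Claim.** The Hypothesis in section 2 is that the platform "significantly increases the appropriateness of referrals to dermatology". Section 3 adds the secondary objective "Reduce and correct the referral of patients with skin conditions from primary care to dermatology". Both describe a change.
- **Design.** Section 4, Study design: "This is a prospective, observational, analytical study of a series of clinical cases". No control arm, baseline period or historical cohort is named anywhere.
- **Capture of the diagnosis.** In section 5, Consultation (primary care), photographs are uploaded and the physician then assesses the patient "through direct observation and guided by the results from the platform. They will enter the diagnosis into the Legit.Health platform". Entry is made "by selecting the condition if it is among the first 5 or by using a drop-down menu". Referral criteria are available on the platform when the physician decides whether to refer.
- **Dermatology side.** Section 5, Consultation (specialist physician), has the Principal Investigator document the primary care physician's initial diagnosis, their own diagnosis, pathology where relevant, and whether the referral was appropriate. It does not say whether that initial diagnosis precedes the platform's output.
- **Main variable.** Section 4, Variables, makes this clinical utility, measured by the Annex I questionnaire at 2 and 4 months. Both time points follow exposure to the tool. Section 5, Patient identification, says that the objective is utility as physicians perceive it and that patients' data will not be analysed.

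**The concern.** A claim that a tool increases something needs an estimate of what would have happened without it. Here every patient is assessed with the tool, and one diagnosis and one referral decision are made with its output available. Whatever agreement or appropriateness rate is found, there is nothing inside the study to subtract from it.

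The hypothesis and the referral objective are at stake. A favourable rate could be reported as confirming the hypothesis when the plan gives no basis for that reading. The loss is also permanent: an unaided judgement that was not written down before the output appeared cannot be recovered afterwards.

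**Working it through.** **1. The plan's own figure.** Section 4, Expected sample size, gives 100 patients, with at least 50 at each of two centres: 2 × 50 = 100, which agrees. No significance level, power or effect size is stated, so nothing further can be reproduced.

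**2. Can the literature serve as comparator?** The Background first gives agreement between primary care physicians and dermatologists of 57% to 65.52%. It later says that "the literature shows a discrepancy of between 55% and 65% between primary care physicians and specialists", which implies agreement of 100 − 65 = 35% to 100 − 55 = 45%. The two ranges do not overlap.

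The first range alone is already too wide. Take n = 100 and an exact one-sided binomial test at 0.025 (assumed, since the plan sets no level):

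- Against 57%, the smallest count r with P(X ≥ r | 0.57) ≤ 0.025 is r = 68 (exact level 1.6%). If unaided agreement is really 65.52% and the tool does nothing, P(X ≥ 68 | 0.6552) = 0.342. A false increase is declared 34% of the time.
- Against 65.52%, r = 76 (exact level 1.6%). If unaided agreement is really 57% and the tool adds 12 points, P(X ≥ 76 | 0.69) = 0.078. The real gain is detected about 8% of the time.

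The 12 points come from the Background's statement of an increase in diagnostic capacity of up to 12%. Reading this as percentage points is an assumption. The quoted benchmark is 65.52 − 57 = 8.5 points wide, not much less than the effect sought.

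**3. What 100 patients can describe.** The 95% half-width for an observed rate of 60% is 1.96 × √(0.6 × 0.4 / 100) = 0.096. That is adequate for an absolute rate but says nothing about change.

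**4. What a paired record would give.** Let ψ be the proportion of patients whose diagnosis changes between right and wrong, and let the net gain be 0.12. The wrong-to-right share among these is π = (ψ + 0.12) / (2ψ). Power = Σ over m of P(M = m | n, ψ) × P(exact two-sided test at 0.05 rejects | m, π).

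| ψ (assumed) | π | Power, n = 100 | Power, n = 60 |
|---|---|---|---|
| 0.16 | 0.875 | 0.854 | 0.565 |
| 0.20 | 0.80 | 0.736 | 0.455 |
| 0.24 | 0.75 | 0.634 | 0.387 |
| 0.30 | 0.70 | 0.525 | – |
| 0.40 | 0.65 | 0.42 | – |

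The n = 60 column illustrates the case where only 60 patients have a reference diagnosis (assumed). All figures concern diagnostic agreement, not referral appropriateness, and ignore clustering by physician.

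**5. A parallel comparator, for contrast.** For 80% power to detect 57% against 69%, 253 patients per arm are needed; for 65.52% against 77.52%, 221 per arm. With 50 per arm, power is 24% to 26%. The paired record is the option that suits the planned size.

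**The case against.** The strongest reply is that the declared primary objective is perceived utility. Annex I asks physicians directly for their view of the tool's impact on accuracy, time and referral efficiency, and that needs no unaided diagnosis. The study is also labelled a proof-of-concept pilot, for which a single arm is a legitimate choice. This stands. A reader might infer that the study can show nothing, or that none of its research questions about help and referral can be addressed. The documents do not support that: perceived help can be described, and the question of whether physicians value the tool is unaffected. The pilot label excuses low power, but not a hypothesis of significant increase with no reference.

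A reader might also infer that the baseline already exists at no cost, because the inclusion criterion reads "Patients with suspected of having the following pathologies in Primary Care". That goes too far. The criterion requires suspicion of a listed pathology. It does not say that a single leading diagnosis has been formed, that suspicion precedes use of the tool, or that any intention to refer exists.

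The initial diagnosis in the specialist's procedures might be meant as unaided. No step captures one, so the wording is ambiguous and does not meet the point.

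Finally, a paired record would not fully test the hypothesis. Appropriateness is described only for patients the dermatologist sees, and no assessment of non-referred patients is arranged. This also stands and limits the fix.

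**Conclusion.** The point holds for the Hypothesis and for the referral objective in section 3. Followed exactly, the plan cannot attribute an objective gain in diagnosis or referral appropriateness to the tool. It does not undermine the questionnaire endpoint, satisfaction, or absolute rates.

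The conclusion rests on the text alone: one capture step, placed after the output, and no comparator. The sizes rest on assumptions: a one-sided 0.025 test against a fixed rate, a 12-point absolute gain, the discordance range, and independent patients. Power at 100 patients falls below 80% by 20% discordance, so the paired analysis should be presented as estimation with an interval rather than as a confirmatory test. It must be corrected for as long as the protocol keeps its claim of a significant increase.

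**What to change.** 1. **Section 5, Consultation (primary care).** Add a first step: before any photograph is uploaded, the physician records and locks the leading unaided diagnosis and the intention to refer (yes/no). The rest proceeds as now. Save the platform's five top-ranked conditions as a study variable.
2. **Section 5, Consultation (specialist physician).** State whether the initial diagnosis is the one made before or after the platform's output.
3. **Analysis.** Estimate the within-patient change in diagnostic correctness against the dermatology or histology diagnosis, as a paired difference with a confidence interval allowing for clustering by physician, among patients with a reference diagnosis. Report how many have one. Report the change in referral intention descriptively only, because appropriateness is not assessed for patients who stay in primary care.
4. **Section 5, Patient identification.** Reconcile the statement that patients' data will not be analysed with the patient-level variables listed in section 4.
5. **If this is not adopted,** restate the Hypothesis and the referral objective as perceived utility or as hypothesis-generating, and remove the claim of a significant increase.

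Earlier e-consultations might give supporting context ("Since June 2020, an asynchronous e-consultation for Dermatology has been available"), but the documents do not show that those records are retrievable or comparable.

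The cost is two fields per patient and a protocol amendment. Committing to a diagnosis first may slightly change how physicians use the tool. Steps 1 to 3 need no added arm; assessing non-referred patients would need extra resources and is not part of this change.
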